7.0 Risks

Venous Blood draw: This is a routine procedure that is considered standard of care in clinical medicine. At the study visit, subjects will undergo venous blood draws. All blood draws will be performed by trained personnel using universal precautions to protect both the subject and personnel. The risks to subjects are minimal, but may include pain, bruising, allergic reaction, infection or bleeding at the needle stick site. A small number of individuals may experience dizziness, lightheadedness or fainting. These usually resolve without any specific medical therapy over the course of minutes to days.

Fingerprick: This is a routine procedure that is considered standard of care in clinical medicine. Each subject will undergo a fingerprick using a sterile, single-use lancet to pierce the skin on the pad of fingertip and extract a single drop of blood. The risks to subjects are minimal, but may include pain, bruising at the puncture site, and/or infection or bleeding at the puncture site. These reactions usually resolve without any specific medical therapy over the course of minutes to days.

Dietary Intervention and Lysine Supplementation: There are no known risks associated with dietary intervention. Lysine is expected to be well-tolerated by all participants. Lysine is used as a dietary supplement, available over the counter, with no known long-term risks. The proposed dose of lysine may cause mild gastrointestinal upset in some subjects. This is expected to be minor and transient.

Stool Sample Collection: There are no known risks associated with stool sample collection. Sample collection may be inconvenient for some individuals.

Private Health Information: This information will be collected during the course of the study. However, only key study personnel will have access to this information, which will be stored in a HIPAA compliant, password protected REDCap database. No protected health information will be shared with employers, insurers, or non-research personnel.

8.0 Reporting of Adverse Events or Unanticipated Problems involving Risk to Participants or Others

Adverse events will be reported to the IRB per Vanderbilt University IRB policy.

9.0 Study Withdrawal/Discontinuation

Subjects may withdraw from the study at any time and should notify study personnel if they wish to withdraw from the study. Subjects may request their biological samples to be destroyed at any time. However, any data or biological samples that have already been used for research cannot be destroyed. Subjects may be discontinued from the study at the discretion of the investigator (possible reasons listed below). Subjects will receive financial compensation for completion of the visit.

Possible reasons for withdrawal/discontinuation from study include, but are not limited to:

- Noncompliance with treatment or procedures
- Decision by participant/participant withdraws consent
- Significant adverse event deemed by investigator to preclude continued participation

10.0 Statistical Considerations

The primary goal is to measure changes in 2-AAA in plasma and urine following dietary intervention study. At 80% power and α =0.05 we require 39 subjects to detect a dietinduced change of 0.5 SD in 2-AAA. Although we expect that a true diet effect would be greater, we have chosen a low threshold to avoid Type 2 error. We expect that individuals in our high and low groups have a significantly different risk of future diabetes. To detect significant differences in disease risk by 2-AAA status at 80% power and α =0.05 (based on 1.6-fold increased risk of diabetes per SD of 2-AAA) we require 76 subjects. These considerations informed our choice to include up to 80 subjects (40 high and 40 low) for the dietary intervention study.

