High baseline plasma 2-AAA in healthy individuals was associated with increased future risk of diabetes (12-year follow-up) in FHS participants and validation samples (N~2,000)⁵. Insulin sensitizing therapy leads to reduction in 2-AAA, but not other putative diabetes-biomarkers, including branched-chain amino acids (BCAAs)¹⁹. Increased 2-AAA is found in skin in the setting of diabetes, as well as in chronic renal failure and sepsis, and increases with age²⁰. Further, decreased urine 2-AAA has been reported in diabetes patients compared with non-diabetic¹⁴, highlighting a likely complex feedback relationship between 2-AAA levels and early diabetes development vs. the setting of established disease. Treatment of overweight/obese adults with impaired fasting glucose or untreated diabetes with pioglitazone (45 mg/day) and metformin (1000 mg twice/day) led to a significant reduction in plasma 2-AAA and lysine, concurrent with an increase in insulin sensitivity¹⁹. Acute insulin infusion (7 hrs) in these subjects also led to a decrease in both lysine and 2-AAA^{19,21}. The epilepsy drug vigabatrin, which acts through GABA transaminase inhibition, leads to increased 2-AAA in plasma and urine, to levels similar to those seen in alpha-aminoadipic aciduria²². Apart from diabetes, 2-AAA has been found to be elevated in the setting of other cardiometabolic or inflammatory diseases including atherosclerosis²³, chronic renal failure and sepsis²⁰, non-alcoholic fatty liver disease (NAFLD)²⁴ and polycystic ovary syndrome (PCOS)²⁵. There is likely some reciprocal regulation between insulin and 2-AAA: insulin infusion in humans leads to decreased 2-AAA^{19,21,26}, while insulin deprivation and hyperglycemia in the setting of type 1 diabetes leads to increased 2-AAA²⁷.

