4.0 Inclusion/Exclusion Criteria

Inclusion Criteria:

- Prior participant in 2-AAA screening study.
- Identified as eligible due to high or low plasma 2-AAA, in the absence of hyperglycemia, as defined by study team.

Exclusion Criteria:

- Individuals who currently use tobacco products.
- Use of prescription or over-the-counter medications or dietary supplements which could modulate levels of 2-AAA and unwilling to discontinue use (from 24 hours prior to first study visit until completion of study). Hormonal birth control is acceptable.
- Follow a severely restricted diet or have food allergies, which would preclude adherence to study diet.
- Newly diagnosed disease (since screening visit), including cardiovascular, renal, or liver disease, or Diabetes mellitus.
- Individuals who are pregnant or lactating
- · Inability to provide written or electronic informed consent
- Inability to fast for 8 hours

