6.0 Study Procedures

The study will be conducted as a randomized crossover dietary intervention, with 4 separate study visits (Figure 4). Individuals will be randomized to normal or high lysine diet for 1 week, followed by a 2-week washout, where participants return to their habitual diet. They will then complete the second 1-week dietary intervention. The entire study period encompasses 4 weeks.

[figure not shown]

Figure 4. Overview of the proposed dietary intervention study.

Screening

Subjects will be screened based on their 2-AAA levels and other data obtained during phase 1 of the study. Inclusion/exclusion criteria will be reviewed to confirm that the subject meets study eligibility requirements. Individuals who meet the inclusion criteria, and do not meet any of the exclusion criteria will be invited to participate in the study. Informed consent will be obtained via telephone with a phone consent witness or electronically. All participants will be instructed to discontinue use of over-the-counter medications and supplements on the day prior to the study visit. Participants will be asked about any major changes to their diet since their screening visit, and if any changes are reported, they will be asked to complete an online food frequency questionnaire (DHQ III) at any time before their visit (Food Frequency Questionnaire Instructions, **Appendix A**). In addition, participants will be asked to complete a 24-hour diet recall (ASA24) around the time of each study visit (Diet Recall Instructions, **Appendix A**). As part of the screening questionnaire, participants will be asked about their physical activity to ascertain their energy requirements for the dietary intervention. Participants will be asked to pick up a stool collection kit from the study coordinator (from the Preston Research Building, or another convenient location) prior to their first visit. If you are a woman and are able to become pregnant, you will have a urine pregnancy test to make sure that you are not pregnant before you receive treatment in this study.

Study Visits

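### One of the two calculations behind N = 80 is power for a difference in diabetes risk, an outcome that the 4-week study does not observe

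*Combined protocol and SAP*

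**What the plan says.** Section 10.0 makes change in plasma and urine 2-AAA after the dietary intervention the primary goal, then gives two sample-size figures, both at 80% power and α = 0.05.

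- **Diet effect:** "we require 39 subjects to detect a dietinduced change of 0.5 SD in 2-AAA".
- **Diabetes risk:** "We expect that individuals in our high and low groups have a significantly different risk of future diabetes". The next sentence begins "To detect significant differences in disease risk by 2-AAA status at 80% power" and arrives at 76 subjects, from a 1.6-fold increase in diabetes risk per SD of 2-AAA.

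The section then concludes: "These considerations informed our choice to include up to 80 subjects (40 high and 40 low) for the dietary intervention study".

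On what is observed, section 6.0 says "The study will be conducted as a randomized crossover dietary intervention, with 4 separate study visits" and "The entire study period encompasses 4 weeks". In the eligibility criteria of section 4.0, diabetes appears among the exclusions: "Newly diagnosed disease (since screening visit), including cardiovascular, renal, or liver disease, or Diabetes mellitus". Section 3.0 reports that high baseline 2-AAA "was associated with increased future risk of diabetes (12-year follow-up) in FHS participants" and in validation samples. Section 12.0 has follow-up in its heading but covers a 5-year study duration and record keeping.

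**The concern.** A power statement says how likely the trial is to detect a given effect on an outcome that it measures. The 76 is worded as one, but its outcome, development of diabetes, is not measured here. The visits include a fingerprick fasting glucose, but no analysis turns it into a disease outcome. The supporting association came from another cohort followed for 12 years.

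A reader could therefore credit the trial with an ability to compare diabetes risk between the high and low groups that it does not have. The figure that does concern the measured endpoint, the 39, is left without the definitions needed to interpret it.

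**Working it through.** **1. Is the disease-risk outcome observed?** Three facts from the protocol settle this: 4 weeks per participant (section 6.0), no diabetes outcome or follow-up visit in any section, and new diabetes since screening as a reason for exclusion (section 4.0). The 5 years in section 12.0 have no participant follow-up attached. The 80% power therefore does not belong to this trial.

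**2. Can the 76 be reproduced?** The only stated input, besides α and power, is 1.6-fold risk per SD. Baseline risk, risk scale and time horizon are not given. I assume that 2-AAA is normally distributed, that 1.6 is an odds ratio, and that the test is a two-sided comparison of two proportions with pooled variance.

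- Mean separation of the two tails in SD, with tail fraction q: D = 2φ(z_q)/q. For q = 10%: 2 × 0.1755/0.10 = 3.51. For q = 25%: 2 × 0.3178/0.25 = 2.54. Section 2.0 mentions both ~10% and 10%-25%.
- High-versus-low odds ratio: 1.6^3.51 = 5.21, or 1.6^2.54 = 3.30.
- Per group: n = [1.960√(2p̄(1−p̄)) + 0.842√(p₀(1−p₀) + p₁(1−p₁))]² / (p₁−p₀)², where p₀ and p₁ are the low- and high-group risks and p̄ is their mean.
- Example, 10% tails and p₀ = 0.10: the odds are 0.111 × 5.21 = 0.578, so p₁ = 0.366 and p̄ = 0.233. This gives n = 38.3 per group, 76.7 in total.

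| Assumed low-group risk | Total, 10% tails | Total, 25% tails |
|---|---|---|
| 20% | 53 | 106 |
| 10% | 77 | 164 |
| 5% | 130 | 289 |

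One set of assumptions lands close to 76, so the figure is not shown to be miscalculated. It cannot be checked from the text, and it moves more than twofold with an input that the text omits.

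**3. What does the 39 imply for the measured endpoint?** The test and sidedness are not stated; I assume a two-sided paired t-test and use the noncentral t distribution.

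- *Taking the 39 at its word.* With n = 39, α = 0.05 and 80% power, the standardised effect (mean contrast divided by its SD) must be 0.46, whichever SD or contrast was meant. At 0.46, power is 81% with n = 40 and 98% with n = 80.
- *Taking 0.5 as the SD of the within-person contrast.* The normal formula gives ((1.960 + 0.842)/0.5)² = 31.4, so 32. The t-test needs 34, and 39 subjects would give 86%, not 80%. Power is 87% with n = 40 and 99% with n = 80.
- *Taking 0.5 as the SD of 2-AAA, one value per diet period, between-visit correlation r.* The standardised effect is 0.5/√(2(1−r)), which equals 0.46 at r = 0.41.
- *The same SD, pre-post changes over four visits, equal correlations.* The standardised effect is 0.5/√(4(1−r)), which equals 0.46 at r = 0.71.
- *Other routes to 39.* Starting from 33 and allowing 15% dropout gives 33/0.85 = 38.8, so 39. A conservative signed-rank allowance (relative efficiency 0.864) also gives 39. Neither is stated.

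**4. High versus low, only if intended.** With 40 per group, a two-sample t-test on the within-person contrast has 80% power at 0.63 SD of that contrast and 60% at 0.5 SD. The plan sets 0.5 SD for the diet effect only; using it here is my benchmark.

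**The case against.** The strongest defence is that the disease-risk sentence only motivates studying the extremes. The sentence before it, about expected risk of future diabetes, supports that softer reading, and section 10.0 says only that the considerations informed the choice of 80. N = 80 also has other support. The top and bottom ~10% of a planned 400 are 0.10 × 400 = 40 each, 80 together. If 39 is meant per group, 2 × 39 = 78 supports 40 + 40 without any diabetes calculation, although the text does not say so. This stands as a defence of the number 80. It does not rescue the wording: as background, the 76 is not a required sample size at 80% power.

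A reader might infer several stronger criticisms that the documents do not support:

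- **That 80 is too few.** Nothing here shows that. On the plan's own 39, power for the diet effect in all 80 is about 98%.
- **That the 39 or the 76 is arithmetically wrong.** Each can be reached under some unstated assumption.
- **That the power for the diet effect is unknown, perhaps as low as 75% in all 80.** That value needs pre-post changes with an assumed correlation of 0.3, a standardised effect of 0.299. Under those inputs 39 subjects would have only 44% power, contradicting the plan. What is missing is the meaning of 0.5 SD, and that is a gap in reporting.
- **That the trial is underpowered for high versus low.** The plan names no such comparison of diet response; its aim concerns responsiveness within the extremes.

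**Conclusion.** The point holds as a minor one. Section 10.0 claims a power for diabetes risk that a 4-week study without a diabetes outcome or follow-up cannot have, and cites it as part of the basis for N. That conclusion rests on the text alone and needs no assumption.

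The dependence of the 76 on baseline risk (totals from 53 to 289 over the ranges shown) rests on assumed risks, normality and an odds-ratio scale. The diet-effect powers rest on a two-sided paired t-test with all 80 completing. The undefined SD, contrast and level of the 39 are missing detail that the same revision should supply; they do not undermine the sample size.

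**What to change.** Keep N = 80 and revise the one paragraph of section 10.0.

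1. Remove the 76 as a basis for N, or relabel it as background for choosing the extremes, without the wording of a required sample size at 80% power.
2. State the power for change in 2-AAA instead. Say which SD the 0.5 refers to, which contrast is used (one value per period or pre-post change), which test and sidedness apply, and whether 39 is overall or per group.
3. Make the printed powers agree with the 39. If the 39 stands, print about 81% in each group of 40 and about 98% in all 80. If 0.5 is the SD of the within-person contrast, correct the 39 to 34 or explain its extra allowance, and print 87% and 99%. If 0.5 is the SD of 2-AAA, give the assumed between-visit correlation.
4. Only if a high-versus-low comparison of diet response is intended, name it and add its sensitivity at 40 per group: 80% power at 0.63 SD of the contrast and about 60% at 0.5 SD.

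The cost is a few sentences and the loss of a printed 80% power figure. Enrolment, visits and assays do not change.

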11.0 Privacy/Confidentiality Issues

Strict confidentiality will be maintained to the fullest extent by the research team, including keeping all data in a secure location. All specimens will be coded anonymously to remain confidential and identifiers will be kept in a separate, secure location. Samples may be shared with third parties outside of Vanderbilt for future testing but will remain anonymous to the recipient. Subjects may contact the principal investigator at any time to request that samples be destroyed.

12.0 Follow-up and Record Retention

Anticipated study duration is 5 years. Research data will be maintained by the PI after study closure. After study closure, research data will be maintained for a minimum of 6 years and possibly indefinitely. Data will be stored on the Vanderbilt University computer network in a password-protected database. Only members of the study team will have

access. Pertinent paper documentation will be kept in locked office and only study personnel will have access. Only personnel directly involved with the study will have access to source data and the electronic database. Genomic data will be deposited in dbGap, a controlled-access database, and will be made available as part of the Policy for Sharing of Data Obtained in NIH Supported or Conducted Genomic Studies. All deposited data and metadata will be documented, per NIH guidelines. All data will be de-identified to protect study participants' identities.

14.0 Appendices

Appendix A

Diet Questionnaire and Recall Instructions

Food Frequency Questionnaire (NCI Diet History Questionnaire (DHQ) III))

At any time following consent, but before your study visit, please complete a food frequency questionnaire. You will be provided with a unique URL to access your questionnaire.

Alternatively, we will provide you with a username and password, and the Study Access Code, which you may use to log in at: http://www.dhq3.org/respondent-login/
You will be given the option to download a Nutrition Report following completion of the questionnaire.

This survey may take you 30-60 minutes to complete.

24-Hour diet recall (NCI Automated Self-Administered 24-Hour (ASA24®) Dietary Assessment Tool)

You will be asked to recall all of the foods and drinks consumed on the day before your study visit, starting at midnight on the day before your visit, and ending at midnight on the day of your study visit. You may complete the assessment in the morning before your study visit, or immediately following your study visit.

The recall can be accessed at: https://asa24.nci.nih.gov/

Please log in with the username and password provided to you by the study coordinator. You will be given the option to download a Nutrition Report following completion of the questionnaire.

This survey may take you 20-30 minutes to complete.
